To establish the feasibility of completing the Catherine Bergego Scale (neglect) (Azouvi et al., 1996), Scale for Contraversive Pushing (SCP) (Karnath et al., 2002) and bucket test (SVV) (Zwergal et al., 2009) in a clinical environment with acute stroke patients to assist with identification of vertical perception loss.

The secondary research questions that this study will aim to address are:

- What percentage of patients admitted to an acute stroke unit show a positive test for vertical perception loss within four weeks of admission (evidence of subjective visual vertical (SVV) tilt on either bucket test or Catherine Bergego Scale or evidence of subjective postural vertical (SPV) tilt on SCP)
- For those able to complete the assessments, does vertical perception loss show any relationship with:
 - Discharge (DC) destination
 - Care package size on discharge
 - Number of inpatient falls
 - Level of functional independence on discharge
- Is there a trend for any element of the SCP or the Catherine Bergego to be more correlated with SVV tilt.

2. Objectives and outcome measures.

Primary objective:

To establish the feasibility of completing the Catherine Bergego Scale, the Scale for Contraversive Pushing (SCP) and the bucket test in a clinical environment with acute stroke patients, to assist with identification of vertical perception loss.

Primary outcomes:

The primary outcome is to understand the feasibility of completing the suite of outcome measures in an acute stroke setting:

- Proportion (%) of patients on whom the assessments are attempted.
- Percentage of patients who are able to complete all three assessments within four weeks of admission.
- Time taken to complete the three measures in an acute clinical setting
- A recommendation regarding the most feasible time point to complete these assessments.

Secondary outputs:

The secondary aims are to gain a further understanding of vertical perception loss in acute stroke patients.

- An understanding of factors that prevent or facilitate completion of these three assessments
- An understanding of healthcare professionals' experiences of completing these assessments in an acute stroke unit.
- An understanding of whether people with stroke (or their advocates) find it appropriate to complete all three assessments in an acute stroke setting.
- Percentage of patients admitted to an acute stroke unit showing a positive test for vertical perception loss within four weeks of admission.

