admission, if still unable they will be attempted again at 2 weeks and 4 weeks post admission. At the point participants complete all 3 outcome measures or at 4 weeks (whichever is earliest) most will have no further active participation in the quantitative part of the study. The assessments do not need to all be completed in one sitting and can be spread across sessions. If a patient is unable to be consented at 48 hours they will be consented as soon after this point as possible up to one week after admission, and this will be recorded. If patients are discharged or have a change in status following consenting to participate but prior to completion of the outcome measures any data collected to date will be utilised in the study results and the reasons for non-completion of the outcome measures will be noted as this will inform the feasibility of these outcome measures. The length of time taken to complete the measures will be recorded by the administrator. The expectation is that administration of all three outcome measures will take no longer than one hour. Due to the observational nature of the SCP and Catherine Bergego Scale elements of these can be completed during therapy sessions. The results and implications of the results of the outcome measures will be discussed with the patient or their advocate should they wish. The impact of the results on the therapists will be explored in a focus group.

At the point the participants are discharged from the stroke unit (this could include but not be restricted to: transfer to another rehabilitation facility, to undergo further neurological observation or intervention, discharge home, to undergo further unrelated medical interventions) their notes will be accessed and the following data extracted:

- Demographic details (age, gender)
- Type and location of stroke
- NIHSS on admission
- Number of in-patient falls
- Discharge (DC) destination
- Level of care required on DC – either care home or size of care package
- Functional ability on DC using the Modified Rankin Scale (MRS) (van Swieten et al., 1988) and the Barthel Index (Mahoney and Barthel, 1965) as these are routinely collected for all patients
- Amount of physiotherapy and occupational therapy received during inpatient stay as submitted to the Sentinel Stroke National Audit Programme (SSNAP). This includes minutes of therapy received per session of therapy, number of sessions of therapy per day and number of days on which therapy was received

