The participant information sheet will make it clear that there is no obligation to participate and that it will not impact their future care. Participants will have the right to withdraw from the study at any point until the time of discharge without detriment and any data already collected up to the point of withdrawal will be utilised in the results.

Confidentiality

All data will be fully anonymised and no participant will be identifiable in any resulting outputs from this research. Data will be stored on a NHS computer or required platforms and anonymised data will be stored on a University of Winchester password protected OneDrive behind a two factor authentication. General Data and Protection Regulations (GDPR) will be followed at all times.

Participants of the focus groups will have the right to withdraw up to the point at which the focus group has been transcribed (10 days after the focus group). At this point the original recording will be deleted, the participants anonymised and withdrawal will not be possible. Anonymised data will be shared with the researcher's supervisory team.

Additional Ethical considerations

All participants will be given information on how to seek support or who to contact to ask questions regarding the research.

If a participant loses capacity during the study any data collected to date will be anonymised and used in the results but no further data would be collected, unless they regain capacity. This is made clear in the participant information sheet and can be discussed with the participant prior to them consenting.

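### Items fixed at admission, including admission NIHSS, are extracted from the notes only at discharge, so consenters who withdraw or permanently lose capacity have no planned record of them

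*Combined protocol and SAP*

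**What the plan says.** **Timing of extraction.** Section 6, Study protocol, sets one trigger: "At the point the participants are discharged from the stroke unit". At that moment "their notes will be accessed and the following data extracted". The list contains age, gender, stroke type and location, and "NIHSS on admission". It also contains falls, destination, care level, MRS, Barthel Index and therapy received. No section describes taking the first group of items earlier.

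**Stopping rules.** Section 10, Withdrawal: "Participants will have the right to withdraw from the study at any point until the time of discharge", and "any data already collected up to the point of withdrawal will be utilised in the results". Section 10, Additional Ethical considerations, on a participant who loses capacity during the study: "no further data would be collected, unless they regain capacity". Section 6 has a similar data-to-date rule for those discharged or changing status before finishing the measures: "any data collected to date will be utilised in the study results", with the reasons for non-completion noted.

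**Use of the data.** Section 8 tabulates descriptors of the participants and takes all consenting patients as the denominator of its main outcome. Section 2 lists among the secondary outputs "An understanding of factors that prevent or facilitate completion of these three assessments".

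**The concern.** Age, stroke type and admission NIHSS exist in the notes on the day a patient consents, when permission to record them is in force. The plan waits until discharge to record them. Anyone whose data collection ends before discharge leaves the study with assessment attempts on file but, as far as the plan goes, without the items that describe their stroke.

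In a feasibility study the people who stop are of interest in their own right. A recorded reason says why someone stopped. It does not say whether those who stopped had a higher admission NIHSS, or a different type or location of stroke, than those who finished. If that cannot be described for part of the consenting group, the completion percentage is harder to carry over to a future study population.

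**Working it through.** No figure in the plan is at issue, so the check is to follow each kind of participant through sections 6, 8 and 10.

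1. **Stays to discharge, measures finished or not.** Extraction takes place. This covers those still unable at four weeks and those whose bucket test is stopped because they find it challenging.
2. **Discharged or transferred before finishing.** Section 6 counts transfer, further intervention and going home all as discharge. Extraction is triggered and nothing is lost.
3. **Loses capacity, then regains it.** The exception in section 10 lets collection resume, so the discharge extraction can go ahead.
4. **Loses capacity and does not regain it.** Section 10 explicitly bars further collection. The only planned extraction lies in the future, so it does not happen.
5. **Withdraws.** The right to withdraw runs until discharge, which is when extraction opens. Every withdrawal therefore precedes extraction. Section 10 keeps what is already held and is silent on later access to the notes, so the natural reading is that extraction does not happen.
6. **Joined through an advocate because capacity was lacking at entry.** The loss-of-capacity clause does not apply. If capacity returns, section 6 requires the participant's own consent to continue. The plan does not say what follows a refusal; if it is treated as a withdrawal, case 5 applies.

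Cases 4 and 5 remain in the denominator of the section 8 main outcome, because they consented. They have no planned value for the admission items.

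**Size.** The documents give no rate of withdrawal, capacity loss or completion. If a share w of consenters stops early, a share c completes, and every early stopper is a non-completer, the share of non-completers without these items is w/(1 − c). With assumed values of w from 5% to 15% and c from 60% to 80%, this runs from 0.05/0.40 = 12.5% to 0.15/0.20 = 75%. All the inputs are assumptions, the upper end pairs the highest stopping rate with the highest completion rate, and the condition that all stoppers are non-completers is itself unsupported. The range shows only that no useful size can be given.

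**The case against.** The strongest reply is that the gap is narrow and touches little that the plan actually analyses. Much of that stands.

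- **Withdrawal.** A stop to later collection is implied, not stated. Only the loss-of-capacity rule is explicit.
- **Factors affecting completion.** A reader might infer that this secondary output would rest only on those who stayed to discharge. It would not. Section 6 records inability to complete any element at the time and notes reasons for non-completion; section 7 documents willingness throughout and gathers therapists' views; section 8 collates reasons for each measure. None of this waits for the notes extraction. Section 8 also plans no comparison of completers with non-completers on the admission items, so such a comparison would be an addition.
- **Direction of bias.** A reader might infer that the described cohort would look milder and more able than the one that consented. The documents do not support this. Patients who lack capacity at entry join through an advocate and are outside the loss-of-capacity clause, so many severe cases may keep their data. Nor can those who stop early be assumed to be mainly non-completers: withdrawal stays open until discharge, and the measures may be finished well before then.
- **No record at all.** This too would be an overstatement. Eligibility checks (section 5) cover adult age and stroke diagnosis. Recruitment logs exist (section 9), with unspecified content. Signing the SVV tilt as contralateral or ipsilesional (section 6, Outcome measures) requires the lesion side to be known. The patient flow diagram is not readable in the text reviewed and no data form was available, so extraction only at discharge is read from the absence of any other stated point.

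What survives is that none of these sources is named as the source of the admission items, and none mentions NIHSS.

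**Conclusion.** The point holds in a limited form. Followed as written, the plan leaves consenters who withdraw, or who permanently lose capacity, in the main denominator without a planned record of age, gender, stroke type and location, or admission NIHSS. The consequences are an incomplete participant table and no means of relating non-completion to stroke severity or type for this group. The main percentage can still be calculated, and the reasons for non-completion are still captured.

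For withdrawal, the conclusion rests on reading the silence in section 10 as a stop; for loss of capacity it rests on explicit text. This is a cheap improvement to data collection, not a defect in the main analysis.

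**What to change.** Divide the extraction in section 6 into two parts.

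- **At consent:** age, gender, stroke type and location, and admission NIHSS.
- **At discharge:** falls, destination, care level, MRS, Barthel Index and amount of therapy.

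In section 8, tabulate the admission items for all consenters and separately for completers and non-completers. In section 10, state what access to the notes, if any, is permitted after withdrawal, and put the same rule in the participant information sheet.

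The cost is a short protocol change, a two-part data form, and opening the notes twice per participant instead of once. No new measurement is needed, and section 9 already has the clinical team both accessing the records and obtaining consent. Discharge items will still be missing for those who stop early; the change does not alter that.

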Neglect will be assessed using the Catherine Bergego Scale (Azouvi et al., 1996). This established outcome measure for neglect is free and observational, it reflects existing practice and therefore reduces the burden on research participants. The scale is a 10-point scale with each item scored between 0 (no neglect) and 3 (severe neglect). The Catherine Bergego Scale has been shown to have excellent inter- and intra-rater reliability (Marques et al., 2019) and excellent construct validity with the Behavioural Inattention Test (Pitteri et al., 2018). See figure 2.

Lateropulsion will be assessed using the Scale for Contraversive Pushing (SCP) (Karnath et al., 2002). This observational assessment can be conducted as part of routine therapy sessions. Scores are assessed in sitting and standing giving a maximum score of 6. The SCP has been found to be a reliable and valid measure (Babyar et al., 2009). The classification used in a recent study (Dai et al., 2021b) will be utilised. Participants will be split into those who are:

- Upright SCP <0.5
- Tilters SCP >0.5 plus score of at least one on one of the three components
- Pushers SCP >3 and score of one all three components

In this study (Dai et al., 2021b) most of those who were upright had a SVV tilt of 0.6° or less and therefore those who are tilters or pushers will be deemed to have a vertical perception tilt.

Scale for Contraversive Pushing (SCP):

A Posture (symmetry of spontaneous posture) Sitting and Standing

Score 1_severe contraversive tilt with falling to the contralesional side

Score 0.75_severe contraversive tilt without falling

Score 0.25_mild contraversive tilt without falling

Score 0_no tilt/upright body orientation

Total (maximum_2)

B Extension (use of the arm/leg to extend the area of physical contact to the ground) Sitting and Standing

Score 1_performed already in rest

Score 0.5_performed only until position is changed^a

Score 0_no extension

Total (maximum_2)

C Resistance (resistance to passive correction of posture to an upright position)^b Sitting and standing

Score 1_resistance is shown

Score 0_resistance is not shown

Total (maximum_2)

^a For sitting, ask the patient to glide the buttocks on the mattress toward the nonparetic side, to transfer from bed to wheelchair toward the nonparetic side, or both. For standing, ask the patient to start walking. If pushing already occurs when the patient is rising from the sitting position, section B is given the value of 1 for standing.

^b Touch the patient at the sternum and the back. Give the following instructions: "I will move your body sideward. Please permit this movement."

	0	1	2	3
1. Forgets to groom or shave the left part of his/her face				
2. Experiences difficulty in adjusting his/her left sleeve or slipper				
3. Forgets to eat food on the left side of his/her plate				
4. Forgets to clean the left side of his/her mouth after eating				
5. Experiences difficulty in looking towards the left				
6. Forgets about a left part of his/her body (eg, forgets to put his/her upper limb on the armrest, or his/her left foot on the wheelchair rest, or forgets to use his/her left arm when he/she needs to)				
7. Has difficulty in paying attention to noise or people addressing him/her from the left				
8. Collides with people or objects on the left side, such as doors or furniture (either while walking or driving a wheelchair)				
9. Experiences difficulty in finding his/her way towards the left when traveling in familiar places or in the rehabilitation unit				
10. Experiences difficulty finding his/her personal belongings in the room or bathroom when they are on the left side				
Total score (/30)				

For people with stroke or their advocates, acceptability of the measures will be assessed throughout. Alongside their ability to complete the outcome measures, their willingness to complete them will be documented. At the point they complete all the outcome measures (or at 4 weeks if they are unable to complete the measures) participants (or their advocates) will be asked, by the therapist completing their measures or a member of the research team, to complete a short survey asking about the acceptability of the outcome measures. The questions will be based on the theoretical framework of acceptability (Sekhon et al., 2017). Participants will be provided with details of the survey in the PIS when they enter the study. Consent to participate in the survey will be taken at the point of entry to the study. Participants will be under no obligation to complete the survey and can participate in the feasibility arm of the study without completing it. The survey will be anonymous and the participant can withdraw up to the point it is completed. Questions will ask about their attitude towards, understanding of and burden of completing the outcome measures. It will be a mix of choice and Likert scale questions with some free text open questions. The survey should take no more than 15 mins to complete. Participants can be supported to complete the survey by an advocate, therapist or member of the research team who can read out the questions and record their responses, but will not influence the answers. The survey will be on paper for ease of completion in the clinical setting.

8. Statistics and Data Analysis

To answer the research questions mainly descriptive statistics will be used and data presented using bar charts and pie charts. The focus group data will be analysed using thematic analysis (Braun and Clarke, 2013).

The percentage of patients who:

- a. are admitted for at least 72 hours and are approached
- b. are approached who agree to participate
- c. agree and can complete the three measures

will be calculated. Demographic data of the participants will be tabulated for display including: number of patients with left or right stroke, number of patients with haemorrhage or infarct stroke, female/male/non-binary/other gender, mean length of stay, location of stroke, median NIHSS on admission, median MRS and Barthel Index on discharge, place of discharge (home/care home/other), care needs on discharge (nil, one, two, three or four calls per day or 24 hour and number of carers required), number of in-patient falls, median minutes of therapy per day (for OT and Physiotherapy) and median number of days on which OT and Physiotherapy were received.

The main outcome will be the percentage of consenting patients who are able to complete the three outcome measures within four weeks of admission. The percentage of patients able to complete each of the outcome measures individually will be calculated to see if one of the outcome measures is more feasible than the others. Reasons for non-completion will be collated for each of the outcome measures and presented using an appropriate tool. The mean time and standard deviation (SD) to complete all three and each individual outcome measure will be presented. To identify the most feasible time point to complete the outcome measures median (and confidence intervals) time to completion of each outcome measure and time to completion of all three outcome measures will be calculated. The percentage of participants completing each or all of the measures at 48 hours, 1 week, 2 weeks and 4 weeks will be presented.

The median scores and confidence intervals for the SCP and Catherine Bergego scale will be calculated, as well as the mean and SD for the bucket test. The percentage of patients with vertical perception loss will be reported – this will be defined as a positive test on one or more of the measures (SVV >2.5°, Catherine Bergego Scale >1, SCP >0.5). For each patient it will be noted if they test positive on one, two or all three measures. This will assist in informing which of the measures will be required in future studies.

To identify trends for vertical perception loss and discharge status narrative statistics will be utilised. For instance the numbers of participants identified as having vertical perception loss who are discharged home will be investigated. If possible a Spearman Rank Correlation with Fisher-Z between outcome measure score and discharge information (e.g. length of stay in days, MRS score or Barthel Score) will be used. These tests have been chosen as the data is ordinal and are expected to be non-

parametric in nature. An ordinal regression will allow identification of which outcome measure is most likely to relate to discharge information.

A Spearman Rank Correlation with Fisher-Z will be completed on each element of the SCP and Catherine Bergego Scale against SVV to identify if any specific elements of the measures are more indicative of vertical perception loss than others. An ordinal regression will allow identification of which elements of the SCP and Catherine Bergego Scale are most likely to relate to SVV tilt.

The percentage of patients able to complete the measures, along with scores and confidence intervals for the outcome measures will be used to determine potential sample size for larger trials (Eldridge et al., 2016) and assess the change in vertical perception loss during in-patient admission.

It is known that neglect (Esposito et al., 2021) and pushing behaviour (Dai et al., 2022) improve over time. Therefore, changes in a sub-sample of the population will be tracked to inform future interventional research. For the subsample who have outcomes taken on discharge a Wilcoxon Sign Rank test will be used to identify the change in scores of the measures during in-patient stay. This will be completed for the whole study population and for each of the subgroups defined as mild, moderate or severe vertical perception loss.

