- To explore the relationship between vertical perception loss and:
 - Discharge destination
 - Care package size on discharge
 - Number of inpatient falls
 - Level of functional independence on discharge
- To explore if any elements of the Catherine Bergego Scale or Scale for Contraversive Pushing show a trend for a relationship to vertical perception loss

3. Trial Design

This is a mixed methods feasibility study with data collected using a cross sectional design, focus groups and surveys. As the nature of acceptability is subjective a qualitative element utilising a phenomenological approach (Nicholls, 2009) will be nested into the study. This will allow an exploration of the experiences of professionals in completing or undertaking the outcome measures via focus groups. People with stroke (or their advocates) acceptability will be explored using a survey, a pragmatic approach to reduce the burden on research participants. Hence, a convergent mixed methods approach will be used (Creswell and Creswell, 2018) to fully answer the research aim and questions.

4. Trial Setting

The population to be studied will be acute stroke patients admitted to a stroke unit. A non-probability, convenience sample will be used. All patients with a diagnosis of stroke admitted for 72 hours to a single stroke unit at Royal Hampshire County Hospital will be considered in the present study.

Calculation of the sample size for a feasibility study is challenging (Hooper, Unknown). Sample sizes of between 24 and 50 participants have been recommended to allow calculation of a sample size for

a full-scale study (Sim and Lewis, 2012, Lancaster et al., 2004, Browne, 1995). Therefore a pragmatic approach to calculating the sample size will be taken. All those admitted to the stroke unit over a six-month period will be eligible for inclusion, meaning approximately 250 people will be screened for participation.

5. Participant Eligibility Criteria

Inclusion and exclusion criteria:

INCLUSION	EXCLUSION
Diagnosis of first stroke by stroke consultant based on clinical or radiographical findings	Under the age of 18
Admitted to stroke unit with a length of stay of over 72 hours	Diagnosis of Transient Ischaemic Attack (TIA)
Ability to consent or an advocate to consent on their behalf	Previous diagnosis of stroke or other neurological diagnosis affecting the brain with residual impairment
Pre-morbid Modified Rankin Scale of less than 4	Patients on an end of life pathway

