	Patients with pre-morbid visual impairment that will not allow them to see the bucket test. Glasses can be worn.
	Inability to speak the English language and no interpreter can be found

6. Trial Procedures

Recruitment

All patients admitted to an acute stroke unit, who meet the inclusion criteria, may be invited to participate. Potential participants will be identified during the daily handover by members of the clinical or research team. Those meeting the inclusion criteria will be approached by a member of the research or clinical team and invited to participate. This will take place between 48 hours and one week after admission. Potential participants will be provided with the participant information sheet (PIS) regarding this study. If the patient is unable to consent due to cognitive or language impairment or low level of consciousness then their advocate will be approached. Where possible potential participants will be supported to consent using information in different formats (e.g.

through use of pictures) or the skill of appropriate members of the clinical team (e.g. speech and language therapists).

The number of people admitted to hospital with stroke who have language or cognitive impairments that may prevent them being able to consent is substantial. To exclude these potential participants would significantly impact the validity and generalisability of the results. Especially as those with significant strokes are more likely to present with vertical perception loss as well as cognitive and language impairment. If they were excluded a large number of patients with vertical perception loss may not be identified. These groups are often underrepresented in stroke research. If someone is unable to consent an advocate will be approached to consent on their behalf.

Those taking consent will decide on capacity. This includes the chief investigator and the stroke research nurse. Both have significant experience working with people with stroke. Both have undergone Good Clinical Practice training and Mental Capacity Act Training. If in any doubt about capacity other members of the healthcare team (e.g., Speech and Language Therapists) can give advice as to whether the potential participant has capacity or whether their advocate should be approached.

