Participants will only be enrolled in the research if an advocate can be found to consent on their behalf. If someone lacks capacity and does not have an advocate they will be ineligible for inclusion in the research. Advocates will be identified through the medical records of the potential participant and will usually be their next of kin or other named contact. They will only be able to consent once they have read a PIS and had time to ask questions of the research team.

On reading the PIS if the patient or their advocate is willing to participate then they will be asked to sign a consent form, by the research team or chief investigator. Potential participants will have a minimum of 12 hours to read the PIS.

If a participant who lacked capacity, and was consented by an advocate, regains capacity then their informed consent to continue will be sought.

Study protocol

For those patients who consent, the qualified physiotherapists or occupational therapists on the stroke unit, will then attempt to complete all 3 outcome measures with the patient (see assessors and outcome measures below). If the patient is unable to complete any elements of the outcome measure for any reason, this will be recorded. If the patient is unable to complete the outcome measures, then an attempt will be made to complete the outcome measures at 1 week post

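### The 48-hour completion row falls before anyone can be tested, and the median time to completion has no rule for participants who never complete or who leave first

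*Combined protocol and SAP*

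**What the plan says.** Section 2 lists among the primary outcomes: "A recommendation regarding the most feasible time point to complete these assessments". Section 8 names two statistics that bear on it. The first is a "median (and confidence intervals) time to completion of each outcome measure and time to completion of all three outcome measures will be calculated". The second is a series of percentages: "The percentage of participants completing each or all of the measures at 48 hours, 1 week, 2 weeks and 4 weeks will be presented".

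The timing rules are in Sections 5 and 6 of the combined protocol and SAP:

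- Eligibility (Section 5): "Admitted to stroke unit with a length of stay of over 72 hours".
- Recruitment (Section 6): "Those meeting the inclusion criteria will be approached by a member of the research or clinical team and invited to participate". On when: "This will take place between 48 hours and one week after admission". On reading time: "Potential participants will have a minimum of 12 hours to read the PIS".
- Study protocol (Section 6): "For those patients who consent, the qualified physiotherapists or occupational therapists on the stroke unit, will then attempt to complete all 3 outcome measures". Repeat attempts follow at 1, 2 and 4 weeks after admission. The same subsection treats 48 hours as the nominal moment of consent, with later consent allowed up to one week after admission.

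On people who do not finish, Section 6 expects some to be discharged or to change status before completing. It says that their data will be used and the reasons noted. Section 10 (Additional Ethical considerations) stops data collection on loss of capacity unless capacity returns. Section 8 defines its main percentage over consenting patients, within four weeks of admission. For the median it states no time origin, estimator or rule for non-completers. For the time-point percentages it does not say whether they are cumulative or which participants form the denominator.

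**The concern.** There are two separate problems. First, the earliest reporting point comes before the earliest time at which the plan's own consent process allows a test, so the row either is empty or means something other than its label. Second, a median time to completion has no obvious value for someone who never completes. The simplest computation drops such people, and that can only move the median earlier or leave it where it is.

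Both statistics feed the recommendation on when to test. Section 8 sets no progression criteria and leaves the feasibility decision to the collated results, so no other pre-set rule would correct a misleading time point. A later study could schedule its assessments on the strength of it.

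**Working it through.** **Timeline.** All inputs are from Sections 5 and 6.

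- Earliest approach: 48 h after admission. Minimum reading time: 12 h. Testing comes after consent.
- Earliest possible attempt: 48 + 12 = 60 h, which is at least 60 − 48 = 12 h after the row's label.
- If the stay of over 72 h must be observed before enrolment, the earliest attempt is after 72 h. If it must be observed before approach, it is 72 + 12 = 84 h, although that reading sits badly with an approach window that opens at 48 h.
- Latest consent: one week = 168 h, which is 168 − 48 = 120 h after the label and coincides with the 1-week attempt. No window separates a late first attempt from the 1-week row.

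On every reading, the share completed by 48 h is 0%.

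**Median.** The plan gives no figure to reproduce and no completion rates. Let F(t) be the cumulative share of all consenting patients who have completed by time t, and c its final value. Among completers only, the distribution is F(t)/c. Since c ≤ 1, F(t)/c ≥ F(t). The observed-times median is where F reaches c/2; the all-consenting median is where F reaches 50%. As c/2 ≤ 50%, the first can never be later than the second.

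The counts below are **assumed**, per 100 consenting patients, as new completions at the first attempt, 1, 2 and 4 weeks. For simplicity, first attempts are taken to precede 1 week.

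| New completions | Cumulative % | c | Observed-times median | All-consenting median |
|---|---|---|---|---|
| 40/20/5/5 | 40, 60, 65, 70 | 70% | first attempt (40 ≥ 35) | 1 week (60 ≥ 50) |
| 20/20/15/5 | 20, 40, 55, 60 | 60% | 1 week (40 ≥ 30) | 2 weeks (55 ≥ 50) |
| 30/10/3/2 | 30, 40, 43, 45 | 45% | first attempt (30 ≥ 22.5) | not reached |
| 30/20/10/10 | 30, 50, 60, 70 | 70% | 1 week (50 ≥ 35) | 1 week from the curve; (7 + 14)/2 = 10.5 days by averaging |

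The last line is a case where the choice matters little.

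Censoring at exit gives a third answer. Assume completions of 25/10/6/4, exits of 15/15/10/15 after each attempt, and a first attempt at day 3. The numbers at risk are 100, 60, 35 and 19. The Kaplan-Meier share not yet completed is 75/100 × 50/60 × 29/35 = 0.518 at 2 weeks, and × 15/19 = 0.409 at 4 weeks. The median is then day 28, against day 3 on observed times and not reached over all consenting patients. Four-week completion is 59% by Kaplan-Meier and 45% of all consenting patients.

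**The case against.** The best defence of the row is that 48 hours is only a name for the first attempt; Section 6 supports this by speaking of consent at 48 hours. That makes the first part largely a matter of labelling. The stay criterion can also be applied afterwards, as a denominator, which is one way to read the approach percentage in Section 8. Both points are fair, but neither gives the row a usable definition: the 60-hour minimum remains, and completions after consent at up to one week would appear under a 48-hour heading.

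On the median, the analysis is mainly descriptive, and completion percentages and reasons for non-completion would appear beside it, so non-completion would not be hidden. Whether leaving counts as failure or is censored is partly a choice of what to estimate, since Section 8 speaks of being able to complete. This stands, and it limits the consequence. It does not supply the missing rule.

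A reader might go further than the documents allow in four ways:

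- **That both defects flatter early testing.** A literal 0% row makes early testing look worse; only the label reading and an observed-times median lean the other way.
- **That the row is out by a known amount.** The 12 h figure, and the 36 h implied by 84 h, are minimum gaps under two readings, not a range.
- **That the first attempt has no time limit.** Testing follows consent, and active participation for most ends at completion or four weeks. What is missing is a target time and a window.
- **That the main outcome is biased.** Its denominator and time limit are stated.

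**Conclusion.** The point holds and should be corrected, but it is limited in reach. The 48-hour row cannot be delivered as written: the plan's own rules put the earliest attempt at 60 hours, or beyond 72 hours if the stay criterion comes first. That part rests only on the documents. The median has no rule for non-completers and leavers. The direction of the observed-times version is certain in the sense that it can never be later than the all-consenting median. By how much it would be earlier here, if at all, is unknown, because every completion count used above is an assumption. If under half of consenting patients complete, an observed-times median would still be reported although the all-consenting median is not reached. The recommendation on time point is exposed to this; the main completion percentage is not.

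**What to change.** - Reconcile Sections 5, 6 and 8 on the timing of approach, consent and first attempt.
- Replace the 48-hour row with a separate result for the first attempt after consent, reported with its actual time from admission (median and range).
- Record the date and time of each attempt and of each measure's completion. Section 6 specifies recording how long administration takes, which does not give the date of completion. As sessions may be split, all three are complete when the last is finished.
- Report cumulative completion by actual time from admission at 1, 2 and 4 weeks, over all consenting patients, with 95% confidence intervals. Place a late first attempt at its actual time, not in an earlier row.
- Beside it, report the share succeeding among those attempted at each scheduled visit. A cumulative curve can only rise, so it cannot by itself show which visit works best.
- Take the median from the cumulative curve over all consenting patients, count those who leave before completing as not completed, and state that it is not reached where that applies. An analysis censoring at discharge may be added as a sensitivity analysis of ability to complete.
- Leave the main outcome's definition, within four weeks of admission, unchanged.

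The cost is protocol and SAP wording, date and time fields for attempts and for each measure's completion (needed from the start of data collection), slightly more analysis, and a median that may be later or not reached.
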